#### **9.4. Vital Signs and Physical Examinations**

Vital signs data will include temperature, respiratory rate, weight, BMI, BSA, systolic and diastolic blood pressures (BPs) and heart rate. Results will be summarized at baseline, each collected postbaseline visit, and change from baseline using descriptive statistics (number of subjects, mean, median, SD, and minimum and maximum values). For subjects who completed study RP103-03, baseline height is taken from the RP103-03 Screening Visit. For subjects who did not complete study RP103-03, baseline height is the last available observation prior to the first dose of study drug in RP103-04.

By-subject listings of vital sign measurements and physical examinations will be presented in data listings.

#### **9.5. Electrocardiogram**

Electrocardiogram data will include heart rate, QRS duration, QRS axis, QT and PR intervals, and QT interval corrected for heart rate using Fridericia method (QTcF). ECG data will be summarized for baseline, each collected postbaseline visit and for the change from baseline to each visit using descriptive statistics (number of subjects, mean, median, SD, and minimum and maximum values) by treatment.

Overall interpretation results for the ECG are classified into 1 of 3 categories: normal, abnormal – not clinically significant, or abnormal – clinically significant. Shift tables will show the number of subjects who had results that shifted from normal, abnormal – not clinically significant, or abnormal – clinically significant at baseline to normal, abnormal – not clinically significant, or abnormal – clinically significant at each collected post-baseline visit.

All ECG data for each subject will be provided in data listings.

#### **9.6. Concomitant Medications**

Concomitant medications are coded using the WHO Drug dictionary (June 2010) . Results will be summarized by Anatomic Therapeutic Class 4th level (ATC-4) and preferred name. If the 4th level term is not available, the next available level (e.g., ATC-3) will be used. All medications with a stop date prior to the first dose of study drug will be considered “prior”. All medications taken on or after the first RP103 dose, regardless of the start date, will be considered “concomitant.”

---

Gastric-acid reducing (GAR) medications were recorded on a separate eCRF from concomitant medications, and will be summarized by ATC-4 and preferred name. The number of occurrences

of each GAR medication will also be summarized by ATC-4 and preferred name. For example, if a subject has two occurrences of a given medication with different start and stop dates, each occurrence will be counted.

The use of concomitant medications and GAR medications will be included in by-subject data listings.

## 10. CHANGES TO PLANNED ANALYSES

The following changes from Amendment 9 of the protocol have been made:

- [REDACTED]
- Use of gastric acid reducing medications was changed from an exploratory endpoint (per the protocol) to a safety endpoint.
- Analysis of annualized exposure adjusted AEs will not be performed.

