
Statistical Analyses:
	
This Study is designed to assess the long-term safety and tolerability and long-term efficacy of RP103 delayed-release cysteamine bitartrate capsules in patients with cystinosis.
 
Assessment Instruments: [REDACTED]
 
Other Determinations:
 
Demographic and disposition data, Study drug administration, medical history, prior and concomitant medications, AEs, clinical laboratory measurements, vital signs, ECG measurements and physical examination findings will be summarized. Descriptive statistics for continuous data will include mean, standard deviation, median, min, max. For discrete data counts and percentages in each category will be tabulated. Descriptive summaries of mean and mean changes from screening will be presented for the safety laboratory parameters (hematology, serum chemistry and urinalysis, as applicable), vital signs and ECGs. The overall incidence of subjects with adverse events will be summarized by System Organ Class (SOC) and Preferred Term (PT) using the latest version of the Medical Dictionary for Regulatory Activities (MedDRA) coding dictionary. Summaries by maximum severity, drug –relationship (as determined by the investigator) and drug discontinuation will also be presented. In addition, summaries of annualized exposure adjusted AE rates as well as summaries of the incidence of subjects with AEs by study year of onset (Year 1, Year 2 and Year 3 or later) will be generated. The overall incidence of subjects with serious adverse events (SAEs) will be summarized by SOC and PT. The annualized exposure adjusted SAE rates as well as the incidence by study year will also be tabulated. Safety laboratory values outside reference ranges will be flagged in laboratory listings.
 
Non-parametric tests will be used to compare mean [REDACTED] domains and summary component scores over time between Screening and last acquired assessment. Trends in gastric acid reducing medications (prescription and OTC) and [REDACTED] [REDACTED]

-------------------------------------	--

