### **11. Statistical Plan**

#### **11.1. Statistical Methods**

This Study is designed to assess the safety and tolerability of Cysteamine Bitartrate Delayed-release Capsules (RP103) in patients with cystinosis.

A statistical analysis plan will be developed that describes in detail, the statistical methods to be used and will be finalized prior to database lock. This document may modify the plans outlined in the protocol; however, any major modifications of the Study endpoint definitions will be reflected in a protocol amendment.

Demographic and disposition data, drug administration, medical history, prior and concomitant medications, AEs, clinical laboratory measurements, vital signs, ECG measurements and physical examination findings will be summarized. Descriptive summaries of mean and mean changes from screening will be presented for the safety laboratory parameters (hematology, serum chemistry and urinalysis, as applicable),

vital signs and ECGs. The overall incidence of subjects with adverse events will be summarized by System Organ Class (SOC) and Preferred Term (PT) using the latest version of the Medical Dictionary for Regulatory Activities (MedDRA) coding dictionary. Summaries by maximum severity, drug –relationship (as determined by the investigator) and drug discontinuation will also be presented. In addition, summaries of annualized exposure adjusted AE rates as well as summaries of the incidence of subjects with AEs by study year of onset (Year 1, Year 2 and Year 3 or later) will be generated. The overall incidence of subjects with serious adverse events (SAEs) will be summarized by SOC and PT. The annualized exposure adjusted SAE rates as well as the incidence by study year will also be tabulated. Safety laboratory values outside reference ranges will be flagged in laboratory listings.

AEs will be categorized using MedDRA, and listed by verbatim, primary term and SOC. SAEs will include MedDRA coding of primary and secondary (non serious) event terms.

[REDACTED]

[REDACTED]

[REDACTED]

[REDACTED]

Cysteamine concentrations and WBC cystine levels will be summarized per patient.

*Pharmacokinetics:*

The steady-state plasma concentration profiles of cysteamine will be determined for each patient and the  $AUC_{0-t}$ ,  $C_{min}$ ,  $C_{max}$ ,  $T_{max}$  and  $t_{1/2}$  PK parameters will be estimated using non-compartmental methods.

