#### 4.2.9. Visit Windows

The visit schedule in Study RP103-04 differed according to whether a subject entered the study after completing Study RP103-03 or entered the study without having previously participated in Study RP103-03 (i.e., Subjects  $\leq$  6years of age and kidney transplant recipients). This difference in visit schedule resulted in each Quarterly visit for subjects from Study RP103-03 occurring, on average, approximately 6 months later in the study than the corresponding Quarterly visit for subjects who did not previously participate in Study RP103-03. For example, the Quarterly 1 visit of a subject from Study RP103-03 generally occurred at approximately 0.75 years in the study, while the Quarterly 1 visit for a subject not previously participating in Study RP103-03 generally occurred at approximately 0.25 years in the study. Two approaches were taken in the analysis to aligning visits for summarization over time:

1. **Collected Visits:** Scheduled Visits (i.e., the visit as recorded on the case report form) were assigned to what is referred to as “Collected Visits” (see
2. Table 2). Summarization using Collected Visits will help to address the approximate 6-month difference between the Quarterly visits for subjects from Study RP103-03 compared to subjects who had not participated in Study RP103-03.

**Table 2: Definition of “Collected Visits” for Subjects Not Previously Participating in Study RP103-03 (Subjects  $\leq$  6 Years of Age and Kidney Transplant Recipients)**

Scheduled Visit		Assigned “Collected Visit” (Label)
Scheduled Visit Number	Scheduled Visit Name	
14	Quarterly 1	Monthly 3
15	Quarterly 2	Monthly 6
16	Quarterly 3	Quarterly 1
17	Quarterly 4	Quarterly 2
18	Quarterly 5	Quarterly 3
19	Quarterly 6	Quarterly 4
20	Quarterly 7	Quarterly 5
21	Quarterly 8	Quarterly 6
22	Quarterly 9	Quarterly 7
23	Quarterly 10	Quarterly 8
24	Quarterly 11	Quarterly 9

Scheduled Visit		Assigned “Collected Visit” (Label)
Scheduled Visit Number	Scheduled Visit Name	
25	Quarterly 12	Quarterly 10
26	Quarterly 13	Quarterly 11
27	Quarterly 14	Quarterly 12
Continues in this pattern for however many Quarterly visits occur		

The table only displays Collected Visits for which the name/label differs from that of the Scheduled Visit.

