### 9.1. Study Drug Exposure

Duration of study drug exposure will be calculated as the duration from the date of first dose of RP103 in Study RP103-04 to the date of last dose as:

Exposure (days) = (Last Dose Date – First Dose Date + 1) – number of days dosed with Cystagon

Duration of exposure will be summarized for each subpopulation and overall using descriptive statistics. The number and percentage of subjects with duration of exposure in each category ( $\leq$  12 months,  $>$  12 months and  $\leq$  24 months,  $>$  24 months and  $\leq$  36 months,  $>$  36 months and  $\leq$  48 months,  $>$  48 months and  $\leq$  60 months, and  $>$  60 months) will also be summarized.

The mean RP103 dose (mg/m^2/day) will be summarized over time using collected visits.

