### 9.2. Adverse Events

Adverse events are coded using the Medical Dictionary for Regulatory Activities (MedDRA) Version 13.0 and displayed in tables and listings using System/Organ/Class (SOC) and Preferred Term.

Summaries of adverse events will be generated for those events that are considered treatment emergent, where treatment emergent is defined as any adverse event that emerges during treatment in study RP103-04, having been absent pretreatment, or worsens relative to the pretreatment state. All adverse event summaries will be presented for each subpopulation and overall.

An overview summary table of AEs will be presented including the number and percentage of subjects reporting a treatment-emergent AE for the following categories:

- Subjects reporting at least one AE
- Subjects reporting at least one treatment-related AE
- Subjects reporting at least one serious AE (SAE)

---

- Subjects reporting at least one Grade  $\geq 3$  AE
- Subjects reporting at least one AE leading to discontinuation of study

The number and percentage of subjects who experienced at least one AE will be summarized overall and for each SOC and each PT. The percentage will be based on the number of subjects in the Safety Population. Each subject will contribute at most one count per summarization category. In other words, if a subject has more than one AE with same PT, the subject will be counted only once for that PT. Similarly, if a subject has more than one AE for a SOC, the subject will be counted only once in that SOC and PT. SOCs (and PTs within each SOC) will be sorted in summary tables by descending frequency of each.

Similarly, the number and percentage of subjects with any treatment-emergent SAEs, with any treatment-emergent adverse events assessed by the Investigator as related to treatment, and with any treatment-emergent adverse events leading to discontinuation of study and with any SAE will be summarized by SOC and PT.

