The number and percentage of subjects with any treatment-emergent adverse events will be summarized by relationship to study drug (not related, unlikely related, possibly related, probably related, definitely related, unknown) and severity (mild, moderate, severe, life-threatening, death, unknown) by SOC and PT. In these tabulations, each subject will contribute only once (i.e., the most related occurrence or the most intense occurrence) to each of the incidence rates in the descriptive analysis, regardless of the number of episodes – e.g. worst grade, per subject, per toxicity.

In addition, summaries of the incidence of subjects with AEs, and SAEs, by study year of onset (Year 1, Year 2 and Year 3 or later) will be generated. Treatment-emergent gastro-intestinal adverse events, i.e. adverse events with SOC of “gastrointestinal disorders”, will also be summarized by frequency of episodes (1-3 occurrences vs 4 or more) by PT. Similarly, treatment-emergent treatment-related gastro-intestinal adverse events will be summarized.

All adverse events occurring on study will be listed in subject data listings.

By-subject listings also will be provided for the following: serious adverse events, adverse events for laboratory abnormalities, and adverse events leading to study discontinuation.

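### SAP 10 drops the protocol's exposure-adjusted AE rates with no visible reason, leaving crude percentages that mix risk with length of follow-up for events that keep accruing

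*SAP*

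**What the plan says.** Protocol 11.1 promises "summaries of annualized exposure adjusted AE rates as well as summaries" by study year of onset. A separate sentence, in the synopsis and again in 11.1, covers serious events: "The annualized exposure adjusted SAE rates as well as the incidence by study year will also be tabulated". Protocol 11.1 also says of the SAP: "This document may modify the plans outlined in the protocol".

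SAP 10, which lists the changes from protocol Amendment 9, says: "Analysis of annualized exposure adjusted AEs will not be performed". It gives no reason in the readable text and does not name the SAE rates.

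SAP 9.2 then reports numbers and percentages of subjects for subpopulations A, B, C and overall, under the rule "The percentage will be based on the number of subjects in the Safety Population". It keeps "summaries of the incidence of subjects with AEs, and SAEs, by study year of onset (Year 1, Year 2 and Year 3 or later"), with no separate denominator stated for those tables. SAP 9.1 derives each subject's days on RP103, net of days on Cystagon, and plans a summary: "The number and percentage of subjects with duration of exposure in each category". The categories run from 12 months or less to more than 60 months.

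On entry and follow-up, RP103-03 completers (A) enrol first, and other patients only after the RP103-03 analysis (Protocol 6.1 and 11.3). SAP 4.2.9 describes the later entrants as those who "entered the study without having previously participated in Study RP103-03", namely children of 6 years or younger and kidney transplant recipients (B and C). Protocol 6.3 sets no fixed end and gives about 96 months as the treatment time.

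**The concern.** The primary objective is long-term safety and tolerability. A percentage of subjects with at least one event has no time scale. If the event keeps accruing, the figure rises with follow-up at unchanged risk, so subjects followed for under a year and subjects followed for more than five years do not belong under one percentage without further information. The same applies when A is read against B or C, should their exposure differ.

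The remaining time-related displays help only in part. The exposure table stands apart from the event counts. The by-year tables have no stated at-risk denominator, and their last class has no upper limit. The reader of the study report could then take a difference in observation time for a difference in safety, or miss a real difference.

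**Working it through.** The documents state no AE rate, person-time or event count for this study, so there is no figure to reproduce. All rates, follow-up times, retention and group sizes in steps 2 to 5 are assumptions; only steps 1 and 6 use figures from the documents.

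**1. Planned maximum follow-up by entry route (Protocol 9.8).** RP103-03 completers: at most 9 monthly and 30 quarterly visits, 9 + 30 × 3 = 99 months. Others: at most 32 quarterly visits, 32 × 3 = 96 months. These are blood-volume maxima, not observed exposure, but they are nearly equal.

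**2. Accruing event, constant rate λ.** Crude percentage = 1 − exp(−λt). Person-time to first event or censoring, per subject = [1 − exp(−λt)]/λ, so the first-event rate is λ at any t.

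| λ per year | Crude, 3 y | Crude, 5 y | First-event rate per 100 PY, either |
|---|---|---|---|
| 0.05 | 13.9% | 22.1% | 5.0 |
| 0.10 | 25.9% | 39.3% | 10.0 |
| 0.20 | 45.1% | 63.2% | 20.0 |

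Over follow-up pairs of 5 v 4, 5 v 3, 6 v 3, 8 v 5 and 5 v 2 years and λ from 0.05 to 0.50, the gap at equal risk is about 4 to 30 percentage points.

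**3. Front-loaded event.** Let F(t) = 0.40 × [1 − exp(−4t)]. The crude figure is 40.0% at both 3 and 5 years, which is right. Person-time per subject is the integral of 1 − F: 3 − 0.40 × 2.75 = 1.90 years and 5 − 0.40 × 4.75 = 3.10 years. One annualized first-event rate is then 0.40/1.90 = 21.1 per 100 PY at 3 years and 0.40/3.10 = 12.9 at 5, a false 1.6-fold difference. Split by year, the rates are 56.2, 1.2 and 0.02 in Years 1, 2 and 3, whatever the total follow-up.

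**4. By-year tables, λ = 0.10.**
- Denominator: Year 1 is 1 − exp(−0.10) = 9.5%. With 70% annual retention, Year 2 over all subjects is 0.70 × 9.5 = 6.7%, a false decline; over those entering Year 2 it is 9.5%.
- Open last class: even among those entering Year 3, the percentage is 1 − exp[−0.10 × (t − 2)], which is 9.5%, 25.9% and 45.1% for follow-up to 3, 5 and 8 years. The first-event rate is 10.0 per 100 PY in all three. An at-risk percentage alone therefore does not repair this class.

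**5. Precision, assuming 40 subjects for 5 years and 20 for 3 years at 0.10.** About 16 first events in 157 PY: 10.2 per 100 PY (exact 95% CI 5.8 to 16.5). About 5 in 52 PY: 9.6 (3.1 to 22.4).

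**6. Clustering of repeat events.** Protocol 4.2.2 reports that 14 of 24 drug-related GI events fell in 2 patients; its Table 7 shows 43 at risk on RP103. The most even allocation consistent with this is 7 + 7 + ten single events. Mean = 24/43 = 0.558. Variance = (49 + 49 + 10 − 24²/43)/42 = 94.6/42 = 2.25. Variance/mean is about 4.0, so a Poisson standard error for total events would be about half the size needed.

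**The case against.** **The change is disclosed and allowed.** This stands: it is no hidden contradiction of the protocol. SAEs are a subset of AEs, so the SAP 10 bullet may be meant to cover the SAE rates. The text does not say so, and permission to change is not a reason for the change.

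**Follow-up may not differ.** A reader might infer from the entry order that A was followed longer than B and C, so that comparisons between them are biased in a known direction. The documents do not support that. Later entry shortens follow-up only if all subjects stop on a common date, whereas Protocol 6.3 also ends participation by patient or physician request, or when the drug becomes available through marketing approval. The planned maxima are about equal and actual exposure by subpopulation is not given. Nor do the exposure categories in SAP 9.1 prove that subjects span them.

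**The dropped measure has its own fault.** This stands (step 3). One annualized rate misleads for early events, where the crude percentage is right.

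**The SAP keeps other displays.** By-year incidence, exposure summaries, GI episode frequency and listings do mitigate. A reader might conclude that at-risk denominators in the by-year tables would then be enough; step 4 shows that they would not be for the open last class.

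**Part of the SAP cannot be read.** Nothing is claimed about the SAP 12.1 table list or the unreadable SAP 10 bullet.

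**Conclusion.** The gap is real in the readable text: AE rates planned in the protocol are withdrawn without a visible reason, the status of the SAE rates is unclear, and no person-time rate replaces them. For accruing events the crude percentages depend on follow-up. Under the assumptions in step 2, equal risk gives 25.9% and 39.3% at 3 and 5 years; events that occur early are little affected.

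That is the possible size of the effect, not an estimate for this study. The size and direction of any difference between A and B or C are unknown, and the documents support no difference between B and C. The study is single-arm and descriptive with exploratory testing only, so the cost is to interpretation. It is an improvement to consider. Confidence is high in the omission and lower in its practical effect.

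**What to change.** In SAP 9.2, beside the crude percentages and not in place of them:

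- Reinstate AE and SAE rates per 100 patient-years on RP103, overall and by subpopulation, for any event, each SOC and common PTs. Use first-event rates, with time censored at the first event, and exact Poisson 95% CIs. Count events over the same RP103 time that SAP 9.1 counts as exposure.
- If total-event rates are shown, give them without a Poisson interval, or with one that allows for clustering within subjects (subject-level bootstrap, robust variance or negative binomial).
- In the by-year AE and SAE tables, use subjects on RP103 at the start of each period as denominator. Add patient-years and first-event rates for each period, saying whether first means first in the study or first in the period. Split the class from Year 3 on, or at least give its patient-years.
- State that one annualized rate over all follow-up falls as follow-up lengthens for front-loaded events, and must be read with the by-year rates.

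If the sponsor keeps the change, SAP 10 should give the reason and say whether the SAE rates remain planned.

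Cost: SAP wording, a few extra tables, and a first-event person-time derivation for each term shown, since SAP 9.1 supplies only total exposure. No new data are needed. Intervals will be wide in small subpopulations, hence the limit to common PTs.

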## 11. TABLES AND LISTINGS CONVENTIONS

Tables and data listings will be created from different SAS programs. A single program may produce multiple tables or multiple data listings from the same dataset (e.g., all clinical chemistry data listings may be generated by a single program).

[figure not shown]
In general, data listings should include all subjects with data. However, if only subjects who meet a certain condition are listed (e.g., subjects with SAEs) and no subjects meet the condition, the data listing will so indicate.

The sort order for data presented in data listings will be by subject number, unless otherwise requested by Horizon Pharma. Within a subject, data will be listed in chronological order. Whenever possible, formatted values will be displayed (i.e., decoded). Where applicable, calendar date and relative day of evaluations/events will be provided in the data listings.

[figure not shown]
---

**12. LIST OF STATISTICAL TABLES, LISTINGS, AND FIGURES TO BE PROGRAMMED**

This figure is a horizontal bar chart consisting of 15 data series. The first series on the left is highly fragmented, with several black blocks of varying widths stacked vertically. The subsequent 14 series are mostly solid black bars, each ending with a small white gap. The bars are set against a background of horizontal white lines.

